### **Randomization**

After the screening has been completed (Phase A), for those who are eligible who have provided informed consent, and who have completed baseline assessments, the (computer) narrator "flips a coin" and randomly assigns participants into control vs. SHE Program conditions (Phase B).

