### Methods - Randomized Pilot Trial

Women who are residents of a battered women's shelter (the Women's Center of Rhode Island [WCRI], Sojourner House, New Hope, or Battered Women's Shelter of Summit and Medina Counties), who are at risk substance users within the 3 months prior to entering the shelter as determined by the screener, the NIDA-Modified ASSIST, and endorse IPV within the 3 months prior to entering the shelter as determined by the screener, the WAST (Phase A) will be eligible for the RCT (Phase B). Phase B will use a two-group, randomized, controlled design with 60 shelter residents. After eligible participants consent to participating in the RCT and complete the computer-based baseline assessments the (computer) narrator will "flip a coin" and randomly assign participants to the SHE Program (an initial session plus booster session within three weeks after the initial session) or to the time and attention matched control condition (an initial session plus a booster session within three weeks after the initial session; both consisting of video viewing of popular shows and preference ratings). Next study participants will complete their assigned computer-based intervention. There will be 3- and 6-month post-shelter computer-based follow up assessments (see figure 2 below).

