### **Potential benefits of the proposed research to the subjects and others**

The potential benefits to women participating in this study include close monitoring of participants' alcohol and drug use as well as participants' increased awareness of community resources for IPV and alcohol and drug-related issues. Half of the participants in this study will not receive any form of an "active" intervention, and thus are unlikely to receive any direct health benefit; however, women in both conditions will receive a list of local substance use treatment referrals and community resources. Half of the participants will receive a brief intervention designed to increase the likelihood of reductions in substance use and IPV, self-change and/or obtaining community resources for alcohol and drug use.

We believe that the risks to participants in this study are very low, particularly given the lack of connection between identifying information and data. We believe that the risks that are present are justified given the tremendous potential of this research to produce a replicable and low-cost motivational intervention that is appropriate for this group. Such an intervention, then, could potentially be presented to unprecedented numbers of persons in a way that is financially

and logistically feasible, potentially leading to beneficial effects for large numbers of substance using women with IPV.

*Importance of the knowledge to be gained.* An exploratory approach towards the development of an effective brief computer-based intervention for sheltered battered women with substance use problems could increase the likelihood of these women accessing services for their substance use difficulties and reducing their substance use and IPV severity. Further, there is promising evidence that the application of brief interventions to substance using women offers substantial benefits to the woman. The paucity of research targeting substance use problems with battered sheltered women and the potential success of implementing a computer-based brief intervention in this population invites the proposed research investigation.

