### **Data Analysis:**

For this treatment development grant, assessment of feasibility and acceptability of the intervention and research procedures is the primary goal. Nonetheless, pilot data can be used to demonstrate whether the effects of treatment look promising across a set of outcome variables, to begin to examine distribution of outcome variables and ranges of correlations among variables across time to inform future analytic strategies, and to suggest, in concert with results from larger scale clinical trials in related fields, the range of effect sizes that would be reasonable to expect in a future trial. As a result, we will obtain the between treatment condition effect size estimates at each assessment (e.g., Cohen's *d* or *h*) as well as the correlation between the same dependent variable at adjacent assessments. We anticipate we will have complete data on approximately 41 participants. Sample size guidelines for treatment development from Rounsaville et al. recommend 15 to 30 participants per cell. Given that group means begin to stabilize by around 15, we believe a sample of ~20-21 in each condition should provide some information relevant to demonstrating potential promise for the intervention.

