Primary analyses will be *intent-to-treat* (using data from all treatment enrollees). Secondary *completer analyses* (including only subjects who attend at least the computer-based session) will also be conducted. Analysis strategies used (hierarchical linear modeling [HLM]) can accommodate missing data, and can be used in a sample of 41 with a highly constrained covariance structure. Outcome variables may be transformed to improve normality if needed. If any outcome variable is too zero-inflated to be normalized through transformation, it will be analyzed with logistic regression or generalized estimating equation techniques in this small pilot study, and then with zero-inflated Poisson or negative binomial regression techniques in the subsequent fully-powered study. We will compare rates of missing data across conditions. Per recent clinical trials guidelines analyses will adjust for baseline levels of dependent variables but will not test or adjust for any other baseline differences between conditions that result from randomization. Participants' data will be directly exported from CIAS to a database immediately after each participant session. CIAS and ACASI data will be backed up daily and checked once per month for out of range values, missing data, and other quality issues.

Study Feasibility and Intervention Feasibility/Acceptability. One of the primary goals of a treatment development study is to demonstrate the feasibility of the proposed treatment and of the study and recruitment methods. As a result, we will assess the feasibility of the research procedures by examining study recruitment and refusal rates, participants' willingness to be randomized, follow-up rates, and range of responses to study questionnaires. We will assess the feasibility and acceptability of SHE by examining rates of intervention attendance, and rates of intervention completion (both the intervention session and booster session for both conditions). For our rates of session completion, we expect at least 80% will complete both baseline and booster sessions based on our good attendance rates in our other IPV intervention studies. We will also examine reasons for termination for consistent patterns. We will examine the acceptability of both SHE and control conditions using data from *Satisfaction with CIAS Software Scale* (i.e., an average score of 4 out of 5 on the CIAS satisfaction scale; at

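### Coin-flip allocation across four shelters secures neither arm balance nor shelter balance, and no planned model includes shelter

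*Protocol*

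**What the plan says.** **Allocation.** The protocol (Methods - Randomized Pilot Trial) states: "Phase B will use a two-group, randomized, controlled design with 60 shelter residents". That section and Randomization describe the mechanism in the same way: once baseline is complete, the narrator tosses a coin and "randomly assigns participants into control vs. SHE Program conditions". No block, stratum or minimisation rule appears in either document.

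**Sites.** Participants are residents of the "Women's Center of Rhode Island [WCRI], Sojourner House, New Hope, or Battered Women's Shelter of Summit and Medina Counties". Expected numbers per shelter are not given.

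**Arm size.** Data Analysis expects complete data on about 41 women. It cites a guideline of 15 to 30 per cell, notes that means start to settle at around 15, and concludes: "we believe a sample of ~20-21 in each condition should provide some information relevant to demonstrating potential promise for the intervention". The SAP repeats the 20-21 figure. The section on potential benefits says: "Half of the participants will receive a brief intervention".

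**Covariates.** The protocol's analyses adjust for the baseline level of the outcome but "will not test or adjust for any other baseline differences between conditions that result from randomization". The SAP (Method) names baseline values of each outcome as covariates and does not mention shelter.

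**The concern.** Shelter is handled neither when women are allocated nor in any stated model. There are reasons within the protocol to think it could matter:

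- Everyone receives usual care from shelter staff, but usual practice on substance use is described for only one of the four shelters.
- A secondary outcome is days of substance use services, which depends on what is available locally.
- The retention argument leans on Rhode Island's small size, yet the Summit and Medina Counties shelter also recruits.

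The trial is small, and its effect sizes are meant to suggest what a later trial could expect. If one arm happens to draw more women from a shelter with different outcomes, part of the observed difference is a shelter difference, and no planned analysis separates the two. Markedly unequal arms would also thin the smaller one, against a plan that reasons in terms of roughly 15 per group or more.

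**Working it through.** **Inputs.** From the protocol: 60 randomised, four shelters, about 41 with complete data, 20-21 per condition, a guideline of 15 to 30 per cell, and 82% retention at 6 months in prior shelter work. Assumed: the coin toss is simple randomisation with probability 0.5, dropout is unrelated to arm, and shelters have the sizes shown below.

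**1. The plan's figure.** 41 × 0.5 = 20.5, so 20-21 per condition reproduces as the 1:1 expectation. The 41 itself does not follow from 60 at 82% (60 × 0.82 = 49.2; 50 × 0.82 = 41). That is a separate matter, so both 41 and 49 are used here.

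**2. Arm size under simple randomisation.** The number in one arm is Binomial(N, 0.5).
- N = 41: SD = √(41 × 0.25) = 3.2; central 95% range 14 to 27; P(20/21 split) = 0.24; P(an arm below 15) = 2·P(X ≤ 14) = 0.060.
- N = 49: 2·P(X ≤ 14) = 0.004.
- N = 60 (all randomised): SD = √(60 × 0.25) = 3.9; 95% range 22 to 38; P(36:24 or worse) = 2·P(X ≤ 24) = 0.155; P(an arm below 15) = 0.00004.

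**3. The same with 30:30 forced at allocation.** The number of completers in one arm is Hypergeometric(60, 30, 41).
- SD = √(41 × 0.25 × 19/59) = 1.8; 95% range 17 to 24.
- P(20/21 split) = 0.42; P(an arm below 15) = 0.0006.

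Blocks within shelters would come close to 30:30 but need not reach it, since an unfinished block of 6 can leave a difference of up to 3 in a shelter.

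**4. Precision.** The variance of the difference is proportional to 1/n₁ + 1/n₂. The half-width for Cohen's d is taken as 1.96·√(1/n₁ + 1/n₂).

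| Split of 41 | 1/n₁ + 1/n₂ | Relative to 20/21 | 95% half-width for d |
|---|---|---|---|
| 20/21 | 0.0976 | 1.00 | 0.61 |
| 16/25 | 0.1025 | 1.05 | 0.63 |
| 15/26 | 0.1051 | 1.08 | 0.64 |
| 14/27 | 0.1085 | 1.11 | 0.65 |

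**5. Shelter splits (assumed sizes).** For a shelter of size n, let p be the probability of a 2:1 or worse split: p = 2·P(X ≤ n/3, rounded down). This gives p = 0.302 for n = 15, 0.099 for 30, 0.344 for 10, 0.375 for 5, 0.044 for 42 and 0.688 for 6. The probability of at least one such shelter is 1 − ∏(1 − p):
- 15/15/15/15: 1 − 0.698⁴ = 0.76
- 30/10/10/10: 1 − 0.901 × 0.656³ = 0.75
- 30/15/10/5: 1 − 0.901 × 0.698 × 0.656 × 0.625 = 0.74
- 42/6/6/6: 1 − 0.956 × 0.3125³ = 0.97

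The 97% is driven by shelters of six, where 4:2 already counts and few women are involved.

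**6. What reaches the estimate.** If one shelter supplies 15 to 30 of the 60 (assumed), its share of the arm differs between arms by 15 percentage points or more in 21% to 25% of trials (exact enumeration over simple randomisation). A 15-point gap passes 15% of that shelter's outcome difference from the other shelters into the unadjusted effect estimate.

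**The case against.** The strongest reply is that nothing here is invalid.

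- Simple randomisation gives no bias in expectation, and between-shelter variation already contributes to the width of the planned 95% intervals.
- If shelter explained 5% of outcome variance (an assumption; range 2% to 10%), removing it entirely would multiply the half-width by √0.95, from 0.61 to 0.60 (range 0.61 to 0.58).
- Feasibility and acceptability are the primary goal, and between-arm tests are exploratory.
- The documents give no shelter-level outcomes, so a shelter effect is plausible but not shown.
- The coin may be participant-facing language for an allocation routine that is not otherwise described.
- Simple randomisation is the least predictable method. Sessions take place on site, and only SHE women can take a Safety Plan print-out, so very short blocks could expose later assignments.

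Most of this stands, and it limits the point to a worthwhile improvement. It does not remove the point. Validity over repeated trials does not help the reader of this one realised effect size, and neither document describes restricted allocation or a place for shelter in the analysis.

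A reader might also infer that the coin toss fails to deliver a promised 20-21 per arm. The documents write the figure as approximate, it equals the expectation, and even a forced 30:30 allocation gives an exact 20/21 split only 42% of the time after dropout. Nor is 15 per cell a minimum set by the plan: it comes from a cited guideline and a remark about when means settle. The primary intent-to-treat analysis is also not confined to complete cases.

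**Conclusion.** The point holds as a gap in the design with a cheap remedy. As written, allocation is unrestricted, and the stated covariates do not include shelter. The arm-size risk is modest: 6% for an arm under 15 with 41 completers, 0.4% with 49, and a variance cost of 5% to 11% for the uneven splits tabulated. Shelter balance is the better reason to act. A 2:1 or worse split somewhere is likely (74% to 97%), though that range rests on assumed shelter sizes and overstates the effect where shelters are tiny.

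Two stronger readings are not supported. One is that adjustment for shelter is expressly barred. The protocol's sentence concerns chance baseline differences in general; it neither names shelter nor addresses design factors, so the accurate statement is that shelter is not provided for. The other is that the effect estimate will be biased. Chance imbalance does not do that in expectation; it affects precision and the interpretation of the single realised estimate.

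The conclusion assumes that the coin toss is literal simple randomisation and that dropout is unrelated to arm.

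**What to change.** Have the software that already randomises draw from a concealed list of permuted blocks of varying size (for example 4 and 6), stratified by shelter. Blocks of 2 should be avoided because they are too easy to predict on site. If some shelters will be very small, collapse the strata to Summit and Medina Counties versus the other three. The documents do not state every shelter's location, so a state stratum cannot be defined from them.

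Amend the covariate sentence in Data Analysis, and the matching SAP text under Method, so that the model includes the stratification factor alongside the baseline outcome (1 degree of freedom if collapsed). This keeps the intent of the existing rule, since a design factor is not an adjustment chosen after seeing imbalance. If unrestricted allocation is intended, say so and give the expected range of arm sizes.

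The cost is a pre-loaded list and two amended sentences. The downside is slightly more predictable allocation than a coin toss, limited by computer concealment, varying block size and blinded research assistants.

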### **The SHE Program condition**

SHE participants will receive a 50-minute intervention after randomization and a 15-minute booster session with three weeks after the initial session on the Tablet PC. (The research team may modify the length of intervention sessions based on open trial feedback). The computer-based intervention and booster session will be conducted in a private space at the battered women's shelter during participants' shelter stay. SHE will take place during participants' shelter stay because women are more likely to initiate changes when they are in a supportive environment.

### **Control condition**

Control group participants will complete the same assessment measures. After randomization, participants in the control condition will receive a 50-minute session and a 15-minute booster session within three weeks after the initial session on the Tablet PC, which will comprise of the viewing of popular entertainers/shows videos. See above for description of the control condition. This condition will control for time spent on the computer-based intervention, maintain blinding of research assistants, and mimic the interactivity of the computer-based intervention condition. The control condition will be conducted in a private space at the shelter during participants' shelter stay.

### **Feasibility**

Our target enrollment of 60 women within an 18 month period appears to be feasible because there are high rates of substance use difficulties among battered sheltered women. Researchers estimate that about 42% of residents of battered women shelters are substance users. Furthermore, we found in our study of a treatment for battered sheltered women with

posttraumatic stress disorder, where women with active substance dependence were ineligible and less likely to be referred to the study, 24% ( $n = 27$ ) of participants assessed at baseline ( $n = 112$ ) still met full criteria for a substance use disorder in the last 3 months. Moreover, there is a relatively high volume of women residents at our recruitment site, and our use of a computer-delivered screener should facilitate disclosure.

## Measures

Participants who screen positive for substance use problems and IPV within the 3 months prior to shelter stay during screening will complete an approximately 20-30 minute baseline assessment session on the Tablet PC. Screening measures for at risk substance use and IPV are the same as the open trial and include the NIDA-Modified ASSIST and the WAST, respectively. Most measures for this study will be completed by participants using the Audio Computer-based Assisted Self-Interview (ACASI) software and the Tablet PC. If there are any technical issues with the Tablet PC, paper copies of the same measures will be offered to participants to complete. Like the data completed on the tablet, the paper versions of the measures will be de-identified data. Measures will be administered to both groups of women at baseline (i.e., after screening and consent) and at 3- and 6 months after shelter discharge. The baseline battery is designed to minimize assessment with the control group in order to take into account growing concerns regarding the motivational properties of assessment, leading to substantial Type II error in other MI-based intervention studies.

**Demographic measures:** All participants will complete demographic information, including age, race, ethnicity, educational level, marital status, occupation, employment (status, # hours per week), socioeconomic status, etc. See Table 1 for the time schedule for the study assessments.

**Acceptability:** *Satisfaction with CIAS Software Scale (SSS)* assesses participant satisfaction on items tapping on likeability, ease of use, level of interest, and respectfulness. Participants will also complete the well-studied 8-item *Client Satisfaction Questionnaire-Revised (CSQ-8-R)* to assess satisfaction with the intervention. These scales will be administered after each computer-based session (i.e., initial session and booster session) and administered to both conditions.

The following measures will be administered to both groups of women at baseline and at 3- and 6- months after leaving the shelter.

**Primary outcome measures:** *Alcohol and Substance use: Timeline Follow-Back (TLFB)-modified computer version* has yielded comparable results to face-to-face interview administrations. The computer-based TLFB will assess drug use and heavy drinking (4+ standard drinks) days for the past week and the past 90 days from entering in the shelter. The TLFB will be done in person as well. For primary analysis, days using drugs and heavy drinking days will be combined to create a single variable that reflects the total number of days that women used drugs or had 4+ drinks. The TLFB has excellent reliability, and is sensitive to change as used in this study. (We will not collect collateral (i.e., from a significant other) reports of subjects' use to corroborate yes/no use of substances because this could pose a risk to confidentiality for the participant, who might be particularly vulnerable if she is experiencing IPV). To provide objective corroboration of self-reported drug use, *hair sample testing* (Psychemedics, Inc) at the 3- and 6-month will be obtained to give an approximately 90-day window of evidence for cocaine, marijuana, amphetamine, or opiate use.

We will report correlations between self-report and biological measures of substance use. *Breath alcohol tests* will be conducted at each follow-up assessment (i.e., at the 3 months and 6 months periods in order to insure that the client has consumed no alcohol prior to the assessment (breath alcohol content < .02). If the participant has been consuming alcohol, the assessment will be rescheduled. Urine drug screen results will also be reviewed to corroborate

self-report data at the 3- and 6- month assessments. Urine drug screens will use the CLIA waived, Inc. Instant Drug Test Cup-7 Panel Cup (ICTC), be unobserved, and test for benzodiazepines, cocaine, methamphetamine, methadone, opioids, oxycodone, and THC. .

Secondary Outcomes: *The Treatment Services Review (TSR)* will be used to assess total days of substance use services (both treatment and self-help utilization) received (including outpatient, day patient, residential treatment, NA, AA) to capture the extent to which women are reaching out to access recovery-related resources. At baseline and at each follow-up point, the TSR will assess total days of substance use services received for a 90 day window.

IPV: The Composite Abuse Scale (CAS) is a widely used self-report of behaviors scale with 4 subscales that measure severe, combined abuse, emotional abuse, physical abuse, and harassment. The CAS has recently been published in the Centers for Disease Control and Prevention compendium of intimate partner violence measures. It consists of 30 items presented in a six point format requiring respondents to answer “never”, “only once”, “several times”, “monthly”, “weekly” or “daily” in a twelve month period.

The Cyber Stalking Scale measure is a 6 –item measure and assesses the use of technologies in stalking and harassment.

Safety Behavior Checklist (SBC) has 15 items that assess the use of strategies suggested to keep victim safe (e.g., hiding money and extra clothing).

*Theorized Mediators: The Confidence Ladder* will be used to assess the participants’ levels of confidence regarding their ability (self-efficacy) to change and abstain from substances. *Readiness Ruler* will be used to assess the degree to which participants’ are ready to cut down or quit alcohol or drugs.

Women who participated in the SHE intervention will complete a computer-based measure at the 3- and 6-month follow-up assessment to determine the extent to which participants achieved their goals on their personalized plan; an indication of the degree to which the SHE intervention had an impact on behavioral change. This measure will follow a similar format to the Effectiveness in Obtaining Resources Scale, which assesses battered women’s effectiveness in obtaining various resources.

At follow up, if a participant is unable to meet in-person to complete the assessments (e.g. participant has moved out of state), she will be given the option of participating in the assessment over the phone. Phone sessions will consist of the research assistant administering all the follow up assessments listed above via a phone session, with the exception of breathalyzer, urine, and hair sample testing.

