least highly satisfied and engaged with software) and CSQ-8-R (i.e., above the average score of 27 on the CSQ-8-R)(see Section C.3.11). We will examine mean, mode, and median scores.

**Other Primary Outcomes.** (1) In addition to examining pre-post changes in the intervention condition, we will calculate the effect size and 95% confidence intervals for number of substance using days [including drug-using and heavy drinking days (4+ standard drinks)]. Exploratory tests for differences between conditions will use HLM, with using days in the 6 months prior to intake as a covariate. (2) **Secondary Outcomes.** We will examine pre-post changes in the intervention condition, and calculate between-groups effect sizes and 95% CIs for (1) total days of treatment received measured by the TSR, and for (2) reduction in IPV severity using the CAS. IPV severity will be operationalized as the sum of the number of abusive acts endorsed on the CAS; a scoring method found to provide a valid measure of abuse severity IPV. For exploratory tests for differences between conditions, we will use HLM with baseline scores as covariates.

**Assessment of processes and individualized treatment response.** This R34 treatment development study is underpowered to explore mediation effects (MacKinnon’s mediation power = 16%); a subsequent R01 will test the hypothesis that improvement in readiness to change and self-efficacy variables partially mediate the effects of SHE on our primary outcomes. Similarly, though a full test of moderation will be conducted in a subsequent R01, we will explore potential predictors of intervention response including IPV severity and baseline substance use severity, and will conduct preliminary examinations of large minority differences in this study.

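### The only specified check of self-reported use against hair and urine is a correlation, which, if pooled, cannot show whether under-reporting differs by arm

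*Protocol*

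**What the plan says.** Under Measures, the Protocol builds its primary outcome variable from the Timeline Follow-Back (TLFB): "days using drugs and heavy drinking days will be combined to create a single variable that reflects the total number of days". Under Data Analysis it plans, for that variable, the "effect size and 95% confidence intervals for number of substance using days", with exploratory between-arm tests by hierarchical linear modelling.

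Three biological measures are taken at follow-up, all described under Measures:

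- **Hair**, "at the 3- and 6-month will be obtained to give an approximately 90-day window of evidence for cocaine, marijuana, amphetamine, or opiate use".
- **Urine**, which will "be unobserved, and test for benzodiazepines, cocaine, methamphetamine, methadone, opioids, oxycodone, and THC". Its use is stated as "Urine drug screen results will also be reviewed to corroborate" self-report, without a statistic or rule.
- **Breath alcohol**, which serves only to confirm sobriety at the visit: "If the participant has been consuming alcohol, the assessment will be rescheduled".

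The one analysis named is "We will report correlations between self-report and biological measures of substance use". The text does not say which coefficient will be used, whether it is computed by arm, or what follows from a poor result. The SAP is silent on all biological measures. Table 1 schedules hair and urine at 3 and 6 months only, and follow-up by phone yields no sample.

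**The concern.** The two arms differ in what they might prompt a woman to report. SHE gives personalised feedback on use and its consequences and offers goal-setting (Study Procedure). Control women watch entertainment videos (Control condition). At both follow-ups, only SHE women complete a measure of how far they met the goals in their plan (Measures). That is a credible route to under-reporting that is heavier in one arm.

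If it happened, it would shift the between-arm effect on using days with no change in behaviour. The trial collects specimens that could give a warning, but the specified analysis does not put them to that use. Neither document defines a discordant report, checks agreement by arm, or compares hair or urine positivity between arms. The effect size matters beyond this pilot: Data Analysis says it will help judge whether effects look promising and suggest a range of effects for a larger trial.

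**Working it through.** The documents give no use rate, SD, hair sensitivity or expected effect, so there is no figure of the plan's own to reproduce. All rates below are assumptions and show direction and order of size only.

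**Step 1. Binary any-use, closed form.** Let p be the true proportion using, equal in both arms; a the under-reporting in control; b the under-reporting in SHE. Assume no false reports of use and a biological test that is always right.

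- h = 2·asin√(p(1−a)) − 2·asin√(p(1−b)); positive values favour SHE.
- Pooled phi = s(1−p) / √(p(1−p)s(1−s)), where s = p(1−(a+b)/2).

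With a = 0.05 and b = 0.20:

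- p = 0.50: reported use is 0.475 vs 0.400, so h = 1.521 − 1.369 = 0.15. s = 0.4375, so phi = 0.21875/0.24804 = 0.88.
- p = 0.70: reported use is 0.665 vs 0.560, so h = 1.907 − 1.691 = 0.22. s = 0.6125, so phi = 0.18375/0.22325 = 0.82.

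With a = 0.10 and b = 0.30, h is 0.21 and 0.28, and phi is 0.82 and 0.74.

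For a given p, pooled phi depends on a and b only through their mean. Swapping the two rates reverses the sign of h and leaves phi unchanged. Setting both to 12.5% gives h = 0 and again phi = 0.88 or 0.82. The pooled figure therefore cannot separate bias for SHE, bias against SHE, and no bias.

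**Step 2. Day count, by simulation with no true effect.** Assumed inputs: 35% abstinent; days used by the others Binomial(90, Beta(0.8, 1.6)), at least 1; probability of a positive hair test 1 − exp(−days/8), or 2% if abstinent. Large-sample results (20,000 per arm), with d positive when it favours SHE:

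| Reporting | d | Pooled r | r, SHE / control | Hair-positive reporting zero days, SHE / control |
|---|---|---|---|---|
| Honest in both arms | 0.00 | 0.72 | 0.72 / 0.72 | 1% / 1% |
| SHE reports 70% of days | 0.29 | 0.70 | 0.71 / 0.71 | 2% / 1% |
| SHE reports 50% of days | 0.52 | 0.65 | 0.70 / 0.72 | 2% / 1% |
| 20% deny all use, SHE only | 0.17 | 0.66 | 0.60 / 0.71 | 21% / 1% |
| 20% deny all use, control only | −0.17 | 0.66 | 0.72 / 0.60 | 1% / 21% |
| 10% deny all use, both arms | 0.00 | 0.66 | 0.66 / 0.66 | 11% / 11% |

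Hair positivity is 53% in each arm throughout. The three denial patterns share one pooled r. The zero-report table exposes denial but not proportional under-counting. For the latter, the useful signal is equal hair positivity alongside a difference in reported days.

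**Step 3. What about 20 women per arm can show.** Data Analysis expects about 41 women with complete data.

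- 95% half-width for d or h at 20.5 per arm: 1.96 × √(2/20.5) = 0.61.
- Sampling SD of pooled r at 20 per arm: about 0.06 to 0.08. Under 20% denial in SHE only, the by-arm gap in r is 0.12 against a sampling SD of about 0.15.
- Power for 10% vs 30% discordance (two-sided 0.05): 35% with 20 per arm, 22% with 12 hair-positive women per arm. Reaching 80% needs 62 per arm.
- Two discordant women out of 12 has an exact 95% interval of 2% to 48%.

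**The case against.** A reader might infer that correlation is the sole check and can reveal nothing. The text does not go that far. Urine is also to be reviewed, although without a method, and the Protocol does not say that the correlation will be pooled. Computed by arm in the Step 1 model, phi would be 0.82 (SHE) vs 0.95 (control) at 50% use and 0.74 vs 0.92 at 70%, so a by-arm correlation could hint at denial. That stands, with two limits: no by-arm calculation is planned, and it barely responds to proportional under-counting.

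A reader might also infer that a false SHE benefit is to be expected. Nothing in the documents shows that. Both arms have the same core assessments, referral lists and brochure. Most measures are self-administered by computer without identifiers, a Certificate of Confidentiality is to be obtained, and research assistants are blinded. Self-report is a declared limitation. These features reduce the risk but do not remove it, because a participant knows what content she saw and the TLFB is also done in person.

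Two further objections stand. The h and phi figures describe any-use with an error-free biological test, not the day count. The goal is feasibility and acceptability, between-arm tests are exploratory, and the SAP says the study is not primarily one of hypothesis testing. That limits the consequence.

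Finally, new tables can mislead. The urine panel covers methadone, benzodiazepines, opioids and oxycodone, and no rule is given for prescribed drugs. SHE aims to increase use of treatment, so counting every positive as use could bias the comparison against SHE. Nor does the Protocol say that the TLFB records days by drug class.

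**Conclusion.** The concern holds in a limited form. Correlation is the only specified analysis of self-report against biology, and a pooled correlation cannot show whether under-reporting differs by arm. Differential under-reporting is a plausible risk, not a demonstrated one, and its direction is not established.

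Under the assumed any-use rates, the spurious effect is h = 0.15 to 0.28 while pooled phi stays at 0.74 or above. In the simulated day count, the patterns that under-report in SHE only give d = 0.17 to 0.52. All of these lie within the 0.61 half-width expected at this sample size, so they would not by themselves produce a convincing finding. They could still colour the effect size carried to the next trial. The change is worth making because it uses specimens already planned. It is not a flaw that invalidates the pilot.

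**What to change.** Keep the correlation, name the coefficient, and report it by arm. Add to the SAP, by arm and visit, as description only:

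1. Hair positivity for cocaine, marijuana, amphetamine and opiates, with the arm difference and 95% CI. This also helps where under-counting is proportional.
2. Among hair-positive women, the proportion reporting zero drug-use days in the matching window of about 90 days, with exact 95% CIs; by drug class only if the TLFB records class.
3. A sensitivity analysis of any drug use by self-report or biological test (Cohen's h, 95% CI). Positives explained by prescribed medication or treatment, including methadone, should be identified and not counted as use; otherwise leave those analytes out.

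State how many women gave no sample, including phone visits, and that hair and urine do not verify heavy drinking. Compare hair with drug days only, not with the combined count. Say plainly that with about 20 women per arm these are checks and not tests.

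The cost is a few extra tables with wide intervals. No new visit or specimen is needed, although item 3 needs either a record of prescribed medication, which the Measures section does not list, or a shorter list of analytes.
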